## **1. List of Abbreviations**

**ACEi** - Angiotensin Convertase Enzyme inhibitors  
**ANOVA** – Analysis of Variance  
**ASCVD** - Atherosclerotic Cardiovascular Disease  
**ARBs** - Angiotensin Receptor Blockers  
**CKD** - Chronic Kidney Disease  
**REDCap** - Research Electronic Data Capture

## 2. Introduction

Chronic diseases, also known as non-communicable diseases, affect many Canadians. In 2021, 45.1% of Canadians lived with at least one major chronic illness (1). Similarly, almost one-third of Albertans have at least one chronic disease (2). Among people over 65 years old, this percentage increases to more than 75% (2).

Adding to the high prevalence of chronic diseases, their management is a difficult task for both the patients and the providers. This is primarily due to the complexity of the diseases and the lack of integrated multidisciplinary approaches to address multiple issues of social determinants of health that people with chronic diseases face (3,4). Lack of these kinds of support leads to poor medication adherence and low self-efficacy (5). Furthermore, many patients do not receive the necessary medications and lifestyle recommendations that could improve their outcomes.

Studies suggest that medication adherence can be improved with education and by removing financial barriers. A randomized control trial conducted by Taibanguay et al. to enhance adherence in rheumatoid arthritis (RA) patients demonstrated that education substantially increased the pill count adherence rate 12 weeks after the interventions (6). In their study, they applied two interventions: a disease information pamphlet and counseling. In both groups, adherence increased from  $92.21 \pm 14.05$  to  $97.59 \pm 10.07$  in the multi-intervention group and from  $88.60 \pm 19.66$  to  $92.42 \pm 14.27$  in the single-intervention group.

Another randomized control trial that evaluated the impact of the elimination of copayments for drugs prescribed after Myocardial Infarction (MI) demonstrated adherence substantially improved after their intervention (7). The study showed a 6% increased adherence in the full-coverage group compared to the usual-coverage group.

## 3. Rationale

Medication non-adherence leads to poor health outcomes (12). One of the pillars of chronic disease management is improving self-efficacy, a capacity to perform behaviors desirable to improved health (13). Higher self-efficacy positively correlates with improved outcomes and reduced healthcare utilization (14).

Cost-related non-adherence in Canada is much higher than in other countries comparable to Canada (15). Copayments and deductibles associated with medications are some of the main reasons why people do not take their medication as prescribed (16).

With the exception of our findings from the ACCESS trial, there is a paucity of evidence on how interventions, including removing financial barriers, might lead to better adherence to medication among people with chronic illnesses in a Canadian context. Even after our initial study was published question remain regarding the mechanism of action of the changes observed. We seek to understand further how the interventions impacted adherence to statins and ACEi/ARBs by assessing and comparing adherence at specific periods after the interventions and how the interventions may have impacted several patient-reported measures related to medication adherence.

#### **4. Objectives**

This secondary outcome analysis aims:

##### **4.1. To determine the effect of two interventions;**

- (a) Elimination of copayment for selected medications that are proven to prevent adverse outcomes such as stroke, heart attacks, and hospitalizations, and
- (b) Comprehensive patient education program targeting lifestyle adjustment and optimal drug use in combination with facilitated relay of information about medication use on patients' beliefs about medication [concerns and needs] and self-efficacy.

##### **4.2. To understand the dynamic changes in medication adherence through time by assessing whether there is a significant difference in adherence at different points during the study period.**

#### **5. Methodology**

##### **5.1. Trial Design**

The trial was designed as a researcher-blinded, parallel, factorial 2x2 pragmatic randomized control trial. Participant blinding was not possible due to the nature of the interventions. The data from the trial will be used to analyze subjects of interest for this secondary outcome analysis paper.

##### **5.2. Interventions**

**a. Elimination of copayments**

We employed a new drug formulary plan that waived the 30% copayment for selected high-value medications. The formulary included statins, beta-blockers, ACE- inhibitors, ARBs, calcium channel blockers, diuretics, anti-platelet agents, anticoagulants, oral hypoglycemics, insulin, and smoking cessation aids.

**b. Patient Education**

We used a combined facilitated relay of information on patient medication use to their healthcare provider. To increase the prescription of beneficial medications, participants who were not on guideline-recommended medications were given a letter to be given to their usual clinicians.

Educational messages tailored to a specific patient's health information were sent through mail or accessed on a password-protected website portal to which they can log on. Patients' preference was requested before the beginning of the study.

The participants in the **control group** neither received the education messages nor had their copayments eliminated.

**5.3. Outcomes**

**a. Beliefs About Medication Questionnaire (BMQ).**

The mean score for BMQ will be calculated for each individual. Then, we will categorize it as 12 or below and over 12. We will also individually calculate the needs and concerns of subscales to localize further where issues arise.

**b. Medication Adherence Self-Efficacy Score (MASES)**

MASES score will be dichotomized and treated as a binary variable. We couldn't find a categorizing threshold from literatures a priori. Therefore, we will conduct a Receiver Operating Characteristic (ROC) analysis to determine a suitable threshold (17).

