**c. Medication Adherence (PDC)**

Adherence to the high-value cardiovascular medications, including Angiotensin Convertase Enzyme (ACE) inhibitors, Angiotensin Receptor Blockers (ARBs), and statins, will be assessed by calculating the proportion of days covered (calculated using the formula below) (sum of days covered in the period of interest (POI))  $\div$  (number of days in the POI)  $\times$  100% (18). Those with 80% or greater PDC are considered adherent, and vice versa.

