#### **5.4.Data source and collection**

Data was collected at baseline, Eighteen months, and end of the study (Thirty-six months). Structured questionnaires were used to collect information about patient-reported outcomes. In addition, the pharmacy information network (PIN) is an objective dataset that will be used to assess medication adherence.

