### 7.5. Outcome analysis

#### Tests for Objective #1:

We will conduct log-binomial regression to estimate the effect of the two interventions on belief about medication and medication self-efficacy and needs concern. Similarly, medication adherence will be analyzed using Robust Poisson Regression.

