6.2. Definition of Medication Adherence

Data extracted from the Pharmacy Information Network will be used to calculate the Proportion of Days Covered (PDC): “number of days dispensed”/“number of days between prescription renewals” (42,43) using drug data in the ICDC Chronic Disease Repository. Patients with medication supplies to cover $\geq 80\%$ of observed treatment days are considered adherent (44,45).

We will calculate PDC for each participant in the initial 12-month period that they were in the trial for both Statins and ACEi/ARBs. For those switching between statins or agents within the ACE/ARB class, ANY dispensed medication in the class will be included in the analysis.

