7.2. Baseline Characteristics

Baseline characteristics will be reported in a Table using descriptive summary statistics. These will be stratified by group assignment, and t-tests/Chi2 tests will be used to examine for inter-group differences in these characteristics.

8. Data Sources

The main data source for the trial will be the ACCESS trial RedCAP database. This contains participant group assignments and all patient reported measures from baseline, 6-month, 18-month, and 33-month surveys. It also contains individuals' unique provincial health number which will permit deterministic linkage to administrative health databases held by Alberta Health (including Alberta Precision Laboratory data, Pharmacy Information Network Data, Practitioner Claims data, Discharge Abstract Database, National Ambulatory Care Reporting System data). All PHNs were verified at the time of study enrollment to be sure that they were accurate and active. In cases where a deterministic linkage is not possible, probabilistic linkage using name, date of birth, and postal code will be used.

9. Interventions (s)

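### The MASES cut rests on an undefined ROC analysis, and no continuous, baseline-adjusted treatment-effect analysis of MASES or BMQ is planned, which costs precision

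*SAP*

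**What the plan says.** SAP Section 5.3.b makes MASES a binary variable, reports that no threshold was found in the literature, and continues: "Therefore, we will conduct a Receiver Operating Characteristic (ROC) analysis to determine a suitable threshold". The reference attached to that step is, by its title, a general introduction to ROC curves.

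For beliefs about medication, SAP Section 5.3.a says: "The mean score for BMQ will be calculated for each individual. Then, we will categorize it as 12 or below and over 12". It adds: "We will also individually calculate the needs and concerns of subscales to localize further where issues arise". No cut is given for the subscales.

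SAP Section 7.5 gives the treatment-effect model: "We will conduct log-binomial regression to estimate the effect of the two interventions on belief about medication and medication self-efficacy and needs concern". SAP Section 7.3 limits adjustment to age, sex and income. SAP Section 7.1 uses the baseline scores only for description. The factorial ANOVA in Section 7.5 concerns medication adherence, not these scores.

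Section 10.5 of the combined protocol and SAP already plans to dichotomise self-efficacy and concerns, with logistic rather than log-binomial regression. The same section analyses the EQ-5D index as continuous by linear regression.

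The two documents list different survey visits. SAP Section 5.4: "Data was collected at baseline, Eighteen months, and end of the study (Thirty-six months". Combined document, Section 8: "all patient reported measures from baseline, 6-month, 18-month, and 33-month surveys"; its Section 4.6 gives the same follow-up times.

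**The concern.** A ROC analysis needs a reference classification, and none is named, so binary MASES is not yet a defined endpoint. The natural candidate is adherence by proportion of days covered (PDC): "Those with 80% or greater PDC are considered adherent, and vice versa". The SAP never links it to the ROC step, so this is an inference. Even then the drug class is open (statins or ACEi/ARBs) and so is the window. The SAP leaves the period of interest open, while Section 6.2 of the combined document uses "PDC for each participant in the initial 12-month period that they were in the trial", which falls after randomisation. The survey visit is open as well.

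Separately, every planned effect estimate for the Objective 1 patient-reported outcomes discards information twice: once by cutting the score, and again by ignoring its baseline value. These are the outcomes meant to explain how the interventions worked, where effects may well be small.

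**Working it through.** **The plan's own figure.** The only sample size stated is for the Poisson primary outcome. With rate 0.14 per year, 3 years, rate ratio 0.88, two-sided 5% and 80% power:
N = [1.96·√4 + 0.8416·√(2 + 2/0.88)]² / (0.42·ln(0.88)²) = 4,667, and 4,667 × 1.01 = 4,714.
It reproduces, but says nothing about MASES or BMQ, for which no power, SD, response rate or correlation is given. Everything below rests on assumed inputs, except that 4,768 randomised (combined document, Section 7.1) gives 4,768/2 = 2,384 per margin of each factor.

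**Loss from cutting.** The relative efficiency of a cut c at quantile q is f(c)²·Var / [q(1−q)]. For a normal score at the median it is 0.3989²/0.25 = 0.637; at an 80/20 split it is 0.490. At the median it is 0.333 for a uniform score, 0.550 for beta(5,2), 0.822 for logistic and 0.961 for t with 5 degrees of freedom.

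**Power** = Φ(d·√(n·eff/2) − 1.96), with n per group. For d = 0.125 SD and n = 1,000:
- continuous: 0.125·√500 = 2.795; Φ(0.835) = 79.8%
- median cut: 0.125·√(500 × 0.637) = 2.230; Φ(0.270) = 60.6%

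| n per group | Continuous | Median cut | 80/20 cut |
|---|---|---|---|
| 500 | 51% | 35% | 28% |
| 1,000 | 80% | 61% | 50% |
| 1,500 | 93% | 78% | 67% |
| 2,384 | 99% | 93% | 86% |

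At 0.2 SD with 1,000 per group the three figures are 99%, 95% and 88%. At 0.3 SD all exceed 99%.

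**Gain from the baseline score.** Replace the variance by 1 − r². At 0.125 SD and 1,000 per group, continuous power rises from 79.8% to 83.4% (r = 0.3), 89.8% (r = 0.5) or 97.5% (r = 0.7).

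**Stability of a ROC cut.** Simulation with binormal scores, 70% adherent, n = 2,000 and the cut at maximum Youden's J. The 95% range of the share classed as high is about 25–79% at AUC 0.55, 32–73% at 0.60 and 43–68% at 0.70. With n = 4,000 at AUC 0.60 it is still about 38–69%.

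**Choice of reference.** With two PDC references (one per drug class), 1,000 per group and AUC 0.58–0.66, the two significance verdicts differ in 14–17% of simulated trials at 0.125 SD, about 4% at 0.2 SD and under 0.3% at 0.3 SD. With no effect, at least one is significant in 6–8%.

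**Type I error.** With 1,900 per margin and no effect, a pooled Youden cut against adherence rejects in 4.9–5.3% of trials, as a fixed cut does (4.7–5.3%).

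**The case against.** Dichotomising was prespecified in Section 10.5 of the combined document, and adjusting only for stratification factors is a stated principle in both documents. Both facts stand, so neither choice can be called an afterthought. Section 10.1 of the combined document does allow further adjustment, but only as a sensitivity analysis after imbalance, and it names neither score.

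Instability of the ROC cut does little to the test itself. In a full simulation at 0.125 SD, a Youden cut gave 60.1% power against 61.8% for a baseline-median cut, with null rejection of 5.6% and 5.4%. This stands: the shifting cut mainly affects what high self-efficacy means and how much the analyst can choose.

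Adding a continuous analysis without ranking it would create a new problem. With r = 0.5 and 1,000 per group, the baseline-adjusted continuous result and a baseline-median binary result disagree on significance in about 31–32% of trials at 0.125 SD. With no effect, at least one is significant in 8–9%. This also stands, and the fix must say which result governs.

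The size of the gain is uncertain. With near-complete response it shrinks to 99% against 93%, and for a heavy-tailed score a median cut loses almost nothing.

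A reader might infer that the open ROC step means inflated false positives. A cut chosen to maximise the difference between arms would reject in 29–31% of null trials, but nothing in the documents suggests that intention. A reader might also infer that the cut was left open with results in hand. The SAP does postdate publication of the main results (SAP Sections 2 and 3), but the documents do not show that MASES or BMQ results by arm were known.

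**Conclusion.** The concern holds as one of precision and definition, not of false positives. Binary MASES cannot be reproduced from the documents as written. In the SAP, every effect on BMQ, its needs and concerns subscales and MASES is binary and unadjusted for a baseline score that the trial holds.

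For an effect near 0.125 SD, a median cut costs about 16 percentage points of power at 500 per group, 19 at 1,000, 15 at 1,500 and 6 at 2,384. This assumes a normal score; the loss fades for larger effects and depends on score shape (median-cut efficiency 33–96%). The ROC criticism applies to MASES only, since the BMQ cut of 12 is fixed. The change is worth making because it is cheap, not because the present plan is invalid.

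**What to change.** 1. **SAP 7.5 and 7.3.** Analyse MASES, the BMQ score that is cut at 12, BMQ needs and BMQ concerns as continuous scores at one named follow-up visit. Use linear regression on both intervention indicators, the stratification factors and the baseline score, with robust standard errors, and report mean differences with 95% confidence intervals. Allow the baseline score as a covariate for these outcomes.
2. **State which result governs for each outcome.** Either the continuous analysis is main and the binary one supportive, with the departure from Section 10.5 of the combined document disclosed as made after the main publication, or the reverse. Do not leave two equal tests at 0.05.
3. **SAP 5.3.b.** Keep binary MASES, but set the cut once, before any comparison by arm, from baseline data with arms pooled and labels hidden. Use one fully defined reference (for example PDC of at least 80% for a named drug class in a stated pre-randomisation window) and one selection rule, such as Youden's J. A baseline-median split is an optional alternative, only if its tie rule cannot leave a group empty. For instance, if half or more score the maximum and ties count as low, nobody is classed as high.
4. **Subscales and visits.** Fix the subscale cuts by the same pre-set rule or do not dichotomise the subscales. Reconcile the survey visits between SAP Section 5.4 and Sections 4.6 and 8 of the combined document.

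The cost is a few short edits and no new data, since SAP Section 7.1 already summarises the baseline scores. The downsides are that results appear on a second scale and that the late addition must be disclosed.

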**c. Medication Adherence (PDC)**

Adherence to the high-value cardiovascular medications, including Angiotensin Convertase Enzyme (ACE) inhibitors, Angiotensin Receptor Blockers (ARBs), and statins, will be assessed by calculating the proportion of days covered (calculated using the formula below) (sum of days covered in the period of interest (POI))  $\div$  (number of days in the POI)  $\times$  100% (18). Those with 80% or greater PDC are considered adherent, and vice versa.

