### 7.4. Subgroup analyses

We have specified the subgroups below to conduct analyses with stratifications. We will calculate the effect and confidence interval for each subset. We included subgroup analysis because there may be a subgroup that would benefit more from these interventions.

- a. Age: >70 years vs 65-69 years
- b. Income group: <30,000 vs >30,000
- c. Financial barriers: Present vs Absent
- d. Condition type: Diabetes // CKD // ASCVD // Risk factors only
- e. Multimorbidity: 1-2 vs 3-4 indicated conditions
- f. Primary Care Relational Continuity: Low/Medium vs High
- g. Specialist Involvement in the Year Before Randomization: Yes vs No
- h. On statin at baseline: Yes vs No
- i. On ACE/ARB at baseline: Yes vs No
- j. Living environment: supported living vs. Independent living
- k. Urban / rural

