4.9. Framework

Two conceptual frameworks influenced the design of this study. First, the health belief model summarizes how and why people make health behaviour choices (33) and includes the constructs of perceived: susceptibility, severity, benefit, and barriers—many of which can be targeted by SMES. Second, the framework proposed by Campbell et al postulates how financial barriers may affect clinical outcomes. These frameworks were used to inform the development of the interventions.

The overarching purposes of the interventions in the ACCESS study will be to:

(1) Increase initiation and adherence to medications that have been proven to reduce the risk of cardiovascular events in this population of high-risk patients, including HMG-CoA reductase inhibitors (Statins) (34) and renin-angiotensin-aldosterone system inhibitors (ACE inhibitors [ACEi] and angiotensin receptor blockers [ARBs]) (35).

(2) Encourage participants to make positive health behavior changes, including healthy dietary choices, engagement in physical activity, cessation of tobacco use, and increased adherence to all preventive medications.

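### The adherence score in SAP 5.3.c mixes starting a drug with staying on it, and its period and denominator are not settled

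*SAP*

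**What the plan says.** SAP 5.3.c defines the proportion of days covered (PDC) for statins and ACEi/ARBs as covered days divided by the "number of days in the POI", and then dichotomises: "Those with 80% or greater PDC are considered adherent, and vice versa". The SAP gives no start, length or number for the POI, and no rule for people who start a drug inside it or never take it. The nearest guide is the Rationale, which speaks of "assessing and comparing adherence at specific periods after the interventions".

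Section 7.5 models adherence with robust Poisson regression, assesses change over time with factorial ANOVA, and puts all analyses on an intention-to-treat basis. Non-users are in the trial: subgroup h in 7.4 is "On statin at baseline: Yes vs No", and subgroup i does the same for ACE/ARB.

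New starts are an intended effect. Under SAP 5.2.b, "participants who were not on guideline-recommended medications were given a letter" for their usual clinician. The framework in section 4.9 of the combined protocol and SAP opens with "Increase initiation and adherence to medications that have been proven".

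Section 6.2 of that document ties the period to trial time: "We will calculate PDC for each participant in the initial 12-month period that they were in the trial for both Statins and ACEi/ARBs". Its ratio, however, uses the interval between renewals as denominator, and its 80% rule refers to days under treatment.

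**The concern.** The education letter works through a clinic visit and a new prescription, so some delay before the first fill is built in. If the POI opens at randomisation and every day counts, that delay is charged against the participant as uncovered time. Once it passes 20% of the period, the participant gets the same score as someone who never started.

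The SAP's Introduction reports only a modest adherence gain with self-management support alongside fewer cardiovascular events, and its Rationale says the mechanism is still open. Starting a drug and taking it more regularly are two obvious candidates, and a single yes/no score cannot separate them. Objective 2 is the most exposed. As first-year starters pass into a fully covered second period, the adherent proportion rises although nobody refills more regularly, and it rises more in an arm with more starts.

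**Working it through.** The documents give no adherence rate, share of new starters, start timing or power for adherence, so there is no figure of the plan's own to reproduce on this point.

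**1. Latest start that can reach 80%.** With start on day s of a period of L days and coverage c afterwards, PDC = c(L − s + 1)/L. Setting PDC ≥ 0.80 gives s ≤ L + 1 − 0.8L/c.

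- L = 365, c = 1: s ≤ 366 − 292 = 74. Day 74 gives 292/365 = 80.0%; day 75 gives 291/365 = 79.7%.
- L = 365, c = 0.95: day 58. c = 0.90: day 41.
- L = 548, c = 1: day 110. L = 1,095, c = 1: day 220.

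The 12-month length comes from section 6.2 of the combined document. The longer periods are assumptions.

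**2. Share of first-year starters credited in period 1** (assumed timing, perfect refills, L = 365).

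- Even over the year: 74/365 = 20%.
- Exponential, mean 60 days, truncated at one year: (1 − e^(−74/60))/(1 − e^(−365/60)) = 71%.
- Exponential with median parameter 30, 60, 90 or 120 days: 82%, 58%, 46% or 40%.

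In period 2 all of them are credited if they continue.

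**3. Rise between periods with no change in refilling.** With even starts, the rise is the share starting × (1 − 74/365). If 2%, 5%, 10% or 15% of all participants start in year 1, the adherent proportion rises by 1.6, 4.0, 8.0 or 12.0 points.

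**4. Illustration of the education contrast.** Assumptions: about 2,380 per margin (4,761/2); 70% of baseline users adherent in both arms; perfect refills after starting; no stopping and no second-year starts. The 50% non-user share is the statin figure for Albertans with chronic disease in the protocol's background, not a figure for enrollees, so 20% is shown as well. Arm proportion = (user share × 0.70) + (non-user share × start rate × share credited). Power is two-sided at 5%, normal approximation.

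| Non-users; starts, control vs education | Outcome | Difference (points) | Power |
|---|---|---|---|
| 50%; 10% vs 20% | Period 1, even starts: 36.0% vs 37.0% | 1.0 | 11% |
| 50%; 10% vs 20% | Period 1, early starts (71%): 38.55% vs 42.10% | 3.55 | about 70% |
| 50%; 10% vs 20% | Period 2: 40.0% vs 45.0% | 5.0 | 94% |
| 50%; 10% vs 20% | Starts among 1,190 non-users per margin | 10 | near 100% |
| 50%; 10% vs 13% | Period 1, even starts: 36.0% vs 36.3% | 0.3 | 6% |
| 50%; 10% vs 13% | Starts among 1,190 non-users per margin | 3 | 63% |
| 20%; 10% vs 20% | Period 1, even starts: 56.4% vs 56.8% | 0.4 | 6% |
| 20%; 10% vs 20% | Period 2: 58.0% vs 60.0% | 2.0 | 29% |
| 20%; 10% vs 20% | Starts among 476 non-users per margin | 10 | 99% |

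The rows on starts answer a different question from the PDC rows. They show what the data could reveal about initiation, not a like-for-like gain in power.

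**5. The two denominators.** Take a perfect user who first fills on day 120 of 365. Under SAP 5.3.c with a trial-time POI, PDC = 246/365 = 67.4%, non-adherent. With the denominator in section 6.2 of the combined document, days before the first fill do not count, so PDC is 100%, adherent. The same person gets opposite scores.

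**The case against.** The strongest reply is that the day-74 limit needs two conditions, and the SAP states only one. It counts all days in the POI, but it never says when the POI opens. If the POI began at first dispensing, or if the denominator in section 6.2 applied, the limit would disappear. This stands, and it is why the finding is conditional. It does not settle the matter. The Rationale and section 6.2 both point to trial time. A denominator starting at first fill would condition on a post-randomisation event that the education arm is meant to change.

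Section 7.5 also does not say that the ANOVA uses the yes/no score. On continuous PDC a late starter gets proportionate credit: with even starts and half non-users, the period-1 difference would be about 0.5 × 0.10 × 0.5 = 2.5 points, not 1.0. A rise to 5.0 points in period 2 would remain.

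A reader might infer that the score hides the starts altogether, or that the later rise is false. The documents support neither. Early starts count at once and later ones can count in the next period. A participant who moves from no drug to continuous supply really does have more covered days. The fault is that coverage gained by starting and coverage gained by steadier refilling share one label.

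Finally, some of the remedy exists. The 'Yes' rows of subgroups h and i come close to an analysis of baseline users, and prescription of indicated medications is a tertiary outcome in section 4.5 of the combined document. But the 'No' rows use the same 80% outcome, and the SAP does not carry initiation among its own outcomes.

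**Conclusion.** The concern holds in conditional form. With an all-days denominator and a POI fixed in trial time, the binary score combines initiation with adherence among users. That can dilute the first-period education effect and produce a later rise driven by starts. The direction follows from the formula. The size does not: it depends on the share of baseline non-users, how many start and when, and how well they refill, none of which the documents give. Across the timings tried, between 20% and 82% of first-year starters with perfect refills are credited in period 1. The power figures are illustrations and should not be read as predictions for this trial.

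What is firm without any assumption is that the POI and the handling of starters and never-users are undefined, and that SAP 5.3.c and section 6.2 of the combined document use different denominators. It would go too far to say that the plan will give a wrong answer. As written, it cannot tell apart two mechanisms that it sets out to understand. This should be changed before the analysis.

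**What to change.** In SAP 5.3.c and 7.5, fix the start, length and number of POIs in trial time, state one denominator, and reconcile it with section 6.2 of the combined document. State how never-users, death and outmigration are handled. Then, for each drug class:

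1. Among participants on the class at baseline, analyse PDC ≥ 80% per period.
2. Among all randomised participants not on the class at baseline, analyse first dispensing by a fixed time that everyone reaches apart from death or outmigration (for example 12 months; minimum follow-up is 2.5 years). State the look-back that defines baseline use.
3. Report mean continuous PDC over all randomised participants beside the 80% cut, so that late starts get proportionate credit.

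Show the Objective 2 time course separately by baseline use, and say whether the ANOVA uses the continuous or the binary measure. Do not replace the intention-to-treat measure with PDC counted from first fill. Baseline use is fixed before randomisation, so the comparisons in items 1 and 2 stay randomised.

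The cost is SAP wording and a few more models on dispensing data already held. The downside is more results per drug class, with items 1 and 2 each on fewer participants.
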